6 STUDY ENDPOINTS

The BENEFIT-02 Study includes the assessment of two primary endpoints and two secondary endpoints that are designed to provide preliminary information regarding the effectiveness and safety of the two study SCS therapies under investigation. There are no formal tests of hypotheses or other pre-specified statistical tests associated with the study primary endpoints.

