6.3 Endpoint Results Example Tables and Figures

The results of primary and secondary endpoints will be analyzed as described in this Statistical Analysis Plan and the Clinical Protocol for the BENEFIT-02 Study.

Example tables and figures representative of how the data will be presented in the final study results are provided below. As applicable, descriptive statistics may also be used to present and summarize the data collected during the study. Means and standard error of the mean will be used to describe results from primary endpoints 1 and 2, and secondary endpoint 1. Change in NRS and Percent Pain Relief (PPR) will be evaluated using paired T-test or two-sample T-test, as applicable. For all analyses, $p < 0.05$ is considered significant. Frequency distributions will be used to describe secondary endpoint 2.

6.3.1 Primary Endpoint 1

Figure 2: Therapy A/B Change in NRS for Pain (Overall) Since Baseline

[figure not shown]
[figure not shown]

Table 2: Primary Endpoint 1 Summary

Numerical Rating Scale for Pain (Overall)	Therapy A n = XX	Therapy B n = XX	Total (A+B) n = XX
Mean NRS at Baseline \pm SEM	X.X \pm X.XX	X.X \pm X.XX	X.X \pm X.XX
Mean NRS at Final Study Visit \pm SEM	X.X \pm X.XX	X.X \pm X.XX	X.X \pm X.XX
Mean Change in NRS \pm SD	X.X \pm X.XX	X.X \pm X.XX	X.X \pm X.XX
Paired T-Test (Final Mean NRS vs Baseline)	p = 0.XXX	p = 0.XXX	-----

Figure 3: Percent Pain Relief (PPR) per Therapy**Table 3: Percent Pain Relief (PPR)**

Percent Pain Relief	Therapy A n = XX	Therapy B n = XX	Therapy (A+B) n = XX
Mean PPR \pm SEM	XX.X% \pm X.XX%	XX.X% \pm X.XX%	XX.X% \pm X.XX%

6.3.2 Primary Endpoint 2

Figure 4: Inter-therapy Comparison

[figure not shown]

Table 4: Inter-therapy Comparison of Change since Baseline

Primary Endpoint 2	Two-Sample T-Test on NRS	Two-Sample T-Test on Percent Pain Relief (PPR)
p value: equal var	X.XXXX	X.XXXX
p value: unequal var	X.XXXX	X.XXXX

6.3.3 Secondary Endpoint 1

Table 5: Secondary Endpoint 1 Summary

Numerical Rating Scale for Pain (Overall)	Therapy A n = XX	Therapy B n = XX	Total (A+B) n = XX
Mean NRS at Study Visit 1 \pm SEM	X.X \pm X.XX	X.X \pm X.XX	X.X \pm X.XX
Mean NRS at Study Visit 3 \pm SEM	X.X \pm X.XX	X.X \pm X.XX	X.X \pm X.XX
Mean Change in NRS \pm SEM	X.X \pm X.XX	X.X \pm X.XX	X.X \pm X.XX
Paired T-Test (Visit 3 Mean NRS vs Visit 1)	p = 0.XXX	p = 0.XXX	-----

6.3.4 Secondary Endpoint 2

Table 6: Investigational Device-Related Adverse Events

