7 ADDITIONAL DATA OF INTEREST

As outlined in the Clinical Protocol for the BENEFIT-02 Study, to supplement the analysis of the study primary and secondary endpoints, additional data of interest will be collected.

Further details regarding how these additional data of interest may be analyzed, and example tables and figures illustrating how the data may be presented are provided below. Frequency distributions will be used to describe adverse events excluded from secondary endpoint 2 and device complaints.

For remote pain assessments, descriptive statistics including means and standard error of the mean will be used to describe results. Comparison of remote and in-office assessments will be performed with a paired T-test, when applicable. For comparison between commercial trials and investigational study phase, overall change in NRS will be evaluated by ANOVA while comparisons between therapies will be evaluated by a paired T-test. Change in NRS between therapies will be evaluated using paired T-test. For all analyses, $p < 0.05$ is considered significant.

7.1 Adverse Events Excluded from Secondary Endpoint 2

Adverse events that are classified by the investigator as related to the SCS trial lead implant procedure, related to the commercial trial period, or related to the investigational device that are not included in secondary endpoint 2 will be summarized.

Table 7: Summary of Adverse Events Excluded from Secondary Endpoint 2

Adverse Event Type	Number of AEs	Subjects with AE, n	Subjects with AE, %
SCS Trial Lead Implant Procedure-Related			
Event type 1	X	X	X.XX%
Event type 2	X	X	X.XX%
Commercial Trial Period Related			
Event type 3	X	X	X.XX%
Event type 4	X	X	X.XX%
Possibly Related to the Investigational Device			
Event type 5	X	X	X.XX%
Event type 6	X	X	X.XX%
Unknown Relationship to the Investigational Device			
Event type 7	X	X	X.XX%
Event type 8	X	X	X.XX%
Total Non-Endpoint Adverse Events	X	X	X.XX%

Number of subjects = XXX

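### The SAP disclaims formal tests for the primary endpoints, then tests them and secondary endpoint 1 at p<0.05 as significant, with no nominal label

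*SAP*

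**What the plan says.** SAP section 6 states: "There are no formal tests of hypotheses or other pre-specified statistical tests associated with the study primary endpoints". Protocol 2.1 says the same and gives the unknown effect size as the reason. Both documents describe a feasibility study whose primary and secondary endpoints give preliminary information.

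SAP 6.3 then says: "Change in NRS and Percent Pain Relief (PPR) will be evaluated using paired T-test or two-sample T-test, as applicable", followed by "For all analyses, $p < 0.05$ is considered significant". Its table shells show where the rule applies:

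- Table 2 (primary endpoint 1) has a row beginning "Paired T-Test (Final Mean NRS vs Baseline", with one p-value for Therapy A and one for Therapy B.
- Table 4 (primary endpoint 2) compares A with B. It has a column headed "Two-Sample T-Test on NRS" and a second column for percent pain relief, each with equal- and unequal-variance p-values.
- Table 5 (secondary endpoint 1) has a row beginning "Paired T-Test (Visit 3 Mean NRS vs Visit 1", again with one p-value per therapy.

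Secondary endpoint 2 is described by frequencies and is not tested. SAP 7, on the additional data, repeats the threshold: "Change in NRS between therapies will be evaluated using paired T-test. For all analyses, $p < 0.05$ is considered significant". (The paired test named there for a between-arm comparison is a separate matter.)

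**The concern.** Section 6 and section 6.3 give the report's author opposite instructions for the primary endpoints. Under section 6, a p-value of 0.03 in Table 4 is not the result of a pre-specified test. Under 6.3 it is a significant result. Nothing says which governs. The disclaimer names only the primary endpoints, so secondary endpoint 1 and the SAP 7 analyses are limited by nothing more than the general description of the study as preliminary. SAP section 5 adds to the ambiguity: it justifies 70 completers by the wish to detect a difference of about two NRS points between therapies, while saying that a statistical sample size calculation is not possible.

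At stake is how the results are read. Any of several contrasts could be reported as significant: A changes pain, B changes pain, A differs from B, or either therapy differs from the score at the end of the commercial trial. The plan does not tell the reader that these p-values are unadjusted.

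**Working it through.** **Plan's own figures.** The documents give no family-wise error rate and no power. The one design calculation that can be reproduced is the attrition chain in SAP section 5, which supplies the sample size:

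- 226 × (1 − 0.51) = 110.7, stated as about 110
- 110 × (1 − 0.15) = 93.5, stated as about 93
- 93 × (1 − 0.25) = 69.75, stated as about 70, or about 35 per therapy

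**Contrasts.** Counting Table 4 once, on NRS, there are five: primary endpoint 1 in A and in B, primary endpoint 2, and secondary endpoint 1 in A and in B.

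**Which nulls can hold together.** Within an arm, primary endpoint 1 is null if the mean final score equals baseline. Secondary endpoint 1 is null if it equals the Visit 1 score. Both hold only if baseline equals Visit 1, meaning no mean change over the commercial trial. Protocol 1.1 places study testing after a successful commercial trial, and SAP section 5 counts failed trials as drop-outs before randomization. So the plausible families of true nulls are:

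- (a) the three primary contrasts: neither therapy changes pain from baseline;
- (b) primary endpoint 2 plus secondary endpoint 1 in both arms: both therapies lower pain equally and the final score matches Visit 1. Primary endpoint 1 is then a true effect and cannot give a false positive.

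**Simple formulas.** Two tests in separate arms are independent: 1 − 0.95² = 0.0975. Three independent tests would give 1 − 0.95³ = 0.143. That overstates family (a), because primary endpoint 2 is built from the same changes as primary endpoint 1. Simulation allows for the shared data.

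**Simulation.** Assumptions: 35 per arm, normal scores, equal variances, two-sided tests (the SAP does not state sidedness), 40,000 replicates per setting. The documents give no correlations between visits, so seven sets were assumed. What matters for (b) and for all five contrasts is the correlation *c* between the two within-subject changes, final minus baseline and final minus Visit 1. Write r_BF, r_BV and r_VF for the correlations baseline–final, baseline–Visit 1 and Visit 1–final:

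c = (1 − r_VF − r_BF + r_BV) / √[2(1 − r_BF) × 2(1 − r_VF)]

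If all three correlations are equal, c = 0.5 whatever their size, so unequal sets are needed to test sensitivity.

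| r_BF, r_BV, r_VF | c | (a) three primary | (b) primary 2 + secondary 1 | all five |
|---|---|---|---|---|
| all equal: 0, 0.3, 0.5 or 0.7 | 0.50 | 11.4–11.8% | 13.6–13.8% | 18.8–19.2% |
| 0.5, 0.2, 0.2 | 0.40 | 11.3% | 14.0% | 19.2% |
| 0.3, 0.6, 0.3 | 0.71 | 11.5% | 13.0% | 17.3% |
| 0.5, 0.9, 0.5 | 0.90 | 11.5% | 12.0% | 15.0% |

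The Monte Carlo standard error is about 0.15 to 0.2 percentage points (for example √(0.12 × 0.88 / 40,000) = 0.0016). Family (a) does not depend on c, so its spread is simulation noise. Counting all eight p-values printed in Tables 2, 4 and 5 instead of five contrasts gives 15.6–19.9%.

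Taken singly, the Therapy A test of primary endpoint 1 rejected in 4.8–5.3% of replicates and the NRS test of primary endpoint 2 in 4.9–5.2%. Each test holds its own level.

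**The case against.** The strongest reply is that this is a feasibility study, described as preliminary in both documents, and such a study need not control family-wise error. That stands. A reader might infer that the plan breaks a promised 5% error rate. It does not: no family-wise level is stated, 0.05 is a per-test threshold, and the tests meet it. The contrasts answer separate questions, and no rule in the text declares success on any one of them or ties a development decision to them.

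A reader might also take the 15–20% for all five contrasts as the headline. The figure is correct arithmetic, but it needs no mean change at any visit, which is implausible after a successful commercial trial.

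A third tempting reading is that the 6.3 sentence overrides section 6, or that the remedy is a formal multiplicity procedure such as Holm. Nothing says which section governs, and adjusted testing would add the formal tests that section 6 and Protocol 2.1 disclaim.

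Two limits also stand. The SAP refers to the protocol for further analysis detail, and the protocol text available here ends at 2.1.5, so the absence of a hierarchy or label is established only for that text. The SAP 7 analyses are supplementary and partly optional, and Table 10 checks agreement between data sources, not efficacy. They are not counted in the rates above.

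None of this removes the contradiction, and the preliminary label does not tell an author whether p<0.05 may be called significant.

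**Conclusion.** The point holds as an internal contradiction with a reporting consequence. It is not a failure of required error control. SAP 6.3 specifies tests and a significance threshold for endpoints that SAP section 6 and Protocol 2.1 say have no such tests. It applies the same threshold to secondary endpoint 1, which the disclaimer does not reach, and SAP 7 repeats it.

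The chance of at least one false significant result is about 12–14% when primary endpoint 2 and secondary endpoint 1 are null, and about 11–12% when the three primary contrasts are null. These are 2.4 to 2.8 times (12.0/5 and 14.0/5) and about 2.3 times (11.5/5) the per-test level. They rest on 35 completers per arm, two-sided tests, normal scores with equal variances and the assumed correlations. This should be corrected because it changes what the report may claim.

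**What to change.** Three changes to the SAP:

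1. In 6.3 and 7, replace the sentence on significance with: *All p-values are two-sided, nominal and unadjusted for multiplicity; they are descriptive and no result will be called statistically significant.*
2. In section 6, extend the statement that there are no formal tests to secondary endpoint 1 and to all SAP 7 analyses.
3. Add 95% confidence intervals for the mean changes and for the A−B difference to Tables 2, 4, 5 and 12. The shells for these tables currently show only means with SEM or SD, and p-values.

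No new data or subjects are needed. A few table shells gain a row, and the intervals come from data already being analysed. The real cost is that the report can no longer describe a single p-value below 0.05 as significant, which is the position section 6 already takes for the primary endpoints.

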7 ADDITIONAL DATA OF INTEREST

As outlined in the Clinical Protocol for the BENEFIT-02 Study, to supplement the analysis of the study primary and secondary endpoints, additional data of interest will be collected.

Further details regarding how these additional data of interest may be analyzed, and example tables and figures illustrating how the data may be presented are provided below. Frequency distributions will be used to describe adverse events excluded from secondary endpoint 2 and device complaints.

For remote pain assessments, descriptive statistics including means and standard error of the mean will be used to describe results. Comparison of remote and in-office assessments will be performed with a paired T-test, when applicable. For comparison between commercial trials and investigational study phase, overall change in NRS will be evaluated by ANOVA while comparisons between therapies will be evaluated by a paired T-test. Change in NRS between therapies will be evaluated using paired T-test. For all analyses, $p < 0.05$ is considered significant.

7.1 Adverse Events Excluded from Secondary Endpoint 2

Adverse events that are classified by the investigator as related to the SCS trial lead implant procedure, related to the commercial trial period, or related to the investigational device that are not included in secondary endpoint 2 will be summarized.

Table 7: Summary of Adverse Events Excluded from Secondary Endpoint 2

Adverse Event Type	Number of AEs	Subjects with AE, n	Subjects with AE, %
SCS Trial Lead Implant Procedure-Related			
Event type 1	X	X	X.XX%
Event type 2	X	X	X.XX%
Commercial Trial Period Related			
Event type 3	X	X	X.XX%
Event type 4	X	X	X.XX%
Possibly Related to the Investigational Device			
Event type 5	X	X	X.XX%
Event type 6	X	X	X.XX%
Unknown Relationship to the Investigational Device			
Event type 7	X	X	X.XX%
Event type 8	X	X	X.XX%
Total Non-Endpoint Adverse Events	X	X	X.XX%

Number of subjects = XXX

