5 SAMPLE SIZE ANALYSIS

The BENEFIT-02 Study is designed to limit the number of subjects involved and the duration of intervention, while ensuring sufficient preliminary data regarding the effectiveness and safety of the study SCS therapies is collected in order to accomplish the study objectives.

Since the effect size of each study SCS therapy on the primary outcome measure (NRS for overall pain) is unknown, statistically driven sample size estimation is not possible. A reduction of approximately two points on an NRS for chronic pain represents a clinically relevant difference.¹

In order to detect a difference of approximately two in mean change in NRS pain score (from baseline to the final study visit) between the two study SCS therapies, a target of 70 subjects should complete the 12 day study stimulation period (~35 subjects for each study SCS therapy).

Therefore, to account for expected attrition due to subject withdrawal following consent but prior to completion of the study testing period:

- Up to 226 subjects will be provisionally enrolled
 - Assumed 51% drop out rate between consent and the randomization visit (e.g. failed commercial trial, withdrawn consent, etc.)
- Approximately 110 subjects will undergo randomization (fully enrolled)
 - Assumed 15% drop out rate following randomization prior to initiation of the assigned study SCS therapy (e.g. subject doesn't meet post-washout inclusion criteria)
- Approximately 93 subjects will initiate the randomly assigned study SCS therapy
 - Assumed 25% drop out rate following initiation of the randomly assigned study SCS therapy (e.g. non-compliance with study assessment schedule, withdrawn consent, subject lost to follow-up, etc.)
- Approximately 70 subjects will complete the study testing period

¹ J. T. Farrar *et al.*, "Clinical importance of changes in chronic pain intensity measured on an 11-point numerical pain rating scale," *Pain*, vol. 94, pp. 149-158, Nov 2001.

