7.3 Remote Pain Assessments

As described in Table 1, remote pain assessments are recorded daily by the subject using the CamNtech PRO-Diary Watch and paper-based Subject Diary. The remotely assessed NRS scores for overall pain collected from the PRO-Diary Watch and Subject Diary may be combined and compared to the In-Office assessments to evaluate the consistency across the in-office and remote data collection settings, and supplement the primary and secondary endpoints.

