7.3.6 Remote Pain Assessments Example Tables and Figures

Table 10: NRS Score Source Comparison

Overall NRS	Baseline/Enrollment (n=XX/XX)	Trial End/Rand (n=XX)	Midpoint Evaluation (Study OV2) (n=XX)	Study Exit (n=XX)
Mean In-Office Assessment \pm SEM	X.X \pm X.XX	X.X \pm X.XX	X.X \pm X.XX	X.X \pm X.XX
Mean Remote Assessment \pm SEM	X.X	X.X \pm X.XX	X.X \pm X.XX	X.X \pm X.XX
Paired T-Test	-----	X.XX	X.XX	X.XX

[figure not shown]
Figure 6: NRS Score Source Comparison

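### The in-office versus remote NRS comparison is meant to assess consistency, but the planned paired t-test addresses only mean shift, not agreement

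*SAP*

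**What the plan says.** SAP 7.3 gives the purpose. Pooled watch and paper-diary scores for overall pain are, optionally, to be "compared to the In-Office assessments to evaluate the consistency across the in-office and remote data collection settings, and supplement the primary and secondary endpoints".

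SAP 7 gives the method: "Comparison of remote and in-office assessments will be performed with a paired T-test, when applicable". It also sets the threshold, "For all analyses, $p < 0.05$ is considered significant", and the descriptive summary: "For remote pain assessments, descriptive statistics including means and standard error of the mean will be used to describe results".

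SAP 7.3.6 shows the planned output, "Table 10: NRS Score Source Comparison". It has a row of in-office means ± SEM, a row of remote means ± SEM, and a paired t-test row filled at trial end/randomization, midpoint and study exit. The baseline cell of the test row is blank. Neither the text nor the table has a mean paired difference, a confidence interval for it, limits of agreement, an intraclass or concordance coefficient, or any other criterion of agreement.

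SAP 5 supplies a yardstick: "A reduction of approximately two points on an NRS for chronic pain represents a clinically relevant difference".

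**The concern.** Consistency between two ways of collecting the same score is a question of agreement: how far apart are the two values for the same subject? The paired t-test answers a narrower question, whether the average difference is zero. That leaves three gaps.

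- Large individual differences in opposite directions cancel and leave no trace in the p-value.
- A p-value of 0.05 or more may mean no shift, or a shift that the data could not resolve.
- A small and uniform shift can be significant although the sources agree closely.

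The printed summaries do not fill the gap. The SEM of each source does not give the SD of the paired differences unless the correlation between the sources is also known, so a reader could not work out agreement from Table 10.

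At stake is how far a reader of the final report may treat remote scores as interchangeable with in-office ones when they are used to supplement the endpoints.

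**Working it through.** **Plan's own figure.** None to reproduce: the SAP states no sample size, power, SD or margin for this comparison. What can be computed is how the planned test behaves.

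**Inputs from the documents**
- Pairs: n = 70, the completers targeted in SAP 5 ("a target of 70 subjects should complete the 12 day study stimulation period (~35 subjects for each study SCS therapy"). Table 10 leaves the actual number open.
- Significance level: 0.05 (SAP 7). Sidedness is not stated; two-sided is assumed.
- Yardstick for a large individual difference: 2 points (SAP 5).

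**Assumptions, shown over a range**
- SD of paired differences: 1.5, 2 or 3, with differences roughly normal.
- True mean shift: 0 or 0.5 points.

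**1. Zero mean shift.** By construction P(p<0.05) = 0.05, so the test is non-significant 95% of the time whatever the SD. The share of subjects differing by more than 2 points is 2 × [1 − Φ(2/SD)], and the 95% limits of agreement are ±1.96 × SD.

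| SD | Share beyond 2 points | 95% limits |
|---|---|---|
| 1.5 | 2 × [1 − Φ(1.33)] = 18% | ±2.94 |
| 2 | 2 × [1 − Φ(1.00)] = 32% | ±3.92 |
| 3 | 2 × [1 − Φ(0.67)] = 50% | ±5.88 |

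The limits are expected to hold 95% of differences; they are not a maximum. An extreme case makes the cancelling plain: 35 subjects at +4 and 35 at −4 give t = 0 and p = 1.00.

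**2. True shift of 0.5 points.** Power comes from the noncentral t distribution with 69 df and noncentrality 0.5 × √70 / SD.

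| SD | Noncentrality | Power |
|---|---|---|
| 1.5 | 2.79 | 0.79 |
| 2 | 2.09 | 0.54 |
| 3 | 1.39 | 0.28 |

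**3. Close agreement can be significant.** Sixty identical pairs and ten differing by 1 point in the same direction give a mean difference of 10/70 = 0.14 and an SD of 0.352. Then t = 0.143 / (0.352/√70) = 3.39, p = 0.001.

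**4. Can 70 pairs support the alternative?** The 95% CI half-width for the mean difference is t(0.975, 69) × SD/√70, with t = 1.995. For each limit of agreement it is 1.995 × SD × √(1/70 + 1.96²/(2 × 69)).

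| SD | Half-width, mean difference | Half-width, each limit |
|---|---|---|
| 1.5 | 0.36 | 0.61 |
| 2 | 0.48 | 0.82 |
| 3 | 0.72 | 1.23 |

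That is precise enough to report usefully.

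**The case against.** The case for leaving the plan alone has real weight.

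- **Nothing depends on it.** SAP 4 bases the primary and secondary endpoints on in-office data. The remote comparison is worded as optional, and the tables are examples. This stands, and it limits the importance of the point.
- **No verdict is defined.** A reader might infer that the SAP will declare the settings consistent whenever p≥0.05. It states no such rule; it only names the test. What remains is that it offers no other criterion, so the p-value is the only formal result on the question.
- **Mean shift is covered.** The test addresses it, and the side-by-side means show its size, so a trivial but significant shift would be seen as trivial. This stands: the method is incomplete for its purpose, not useless.
- **Power is not necessarily poor.** A reader might infer that the test will usually miss a real shift. At 70 pairs that depends on an unknown SD: power for 0.5 points is 0.79 at SD 1.5, and for a 1-point shift at that SD it is above 0.999. Low power is a possibility, not an established result.
- **Some of the difference may be real.** SAP 7.3.2 notes that watch values may be averages, and Protocol 1.4.1 schedules them twice daily. Part of any within-subject difference may be pain varying over the day. That affects how limits of agreement are read, not whether they should be shown.
- **Figure 6 is not available for review.** It could contain an agreement plot, but no text describes one.

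A reader might also infer that Table 10 licenses the later analyses, since Table 11 sets an in-office baseline against remote scores. SAP 7.4 does not make that comparison conditional on Table 10. The two-day score in SAP 7.3.3 is moreover the second-lowest daily value in a phase, not a score matched to a visit.

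**Conclusion.** The point holds as a gap between purpose and method. The stated purpose is "to evaluate the consistency across the in-office and remote data collection settings", and the planned analysis can speak only to a mean shift. That conclusion follows from what a paired t-test does and needs no assumption.

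The illustrative sizes do rest on assumptions: 70 pairs, two-sided testing, roughly normal differences and SDs of 1.5 to 3. Within that range, between 18% and 50% of subjects could differ by more than 2 points with the test non-significant 95% of the time.

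The documents do not support saying that an endpoint is compromised, that the SAP will report a false finding of consistency, or that the test is underpowered at its planned size. This is a worthwhile, low-cost improvement to a supplementary analysis.

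**What to change.** In SAP 7 and Table 10, at each time point with paired data:

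1. Add the mean paired difference (remote minus in-office) with its 95% CI.
2. Add Bland-Altman 95% limits of agreement, preferably with their own CIs, and read them against the 2-point relevant difference in SAP 5.
3. State that p≥0.05 is not to be interpreted as consistency.

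The t-test row may stay, labelled as a check for mean shift.

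A pass/fail margin on the CI of the mean difference is not recommended, because it too would judge only the mean. With zero observed mean difference, SD 4 and 70 pairs, the CI is ±1.995 × 4/√70 = ±0.95, inside a ±1-point margin, while the limits of agreement are ±1.96 × 4 = ±7.84.

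The cost is a few table rows and a sentence or two of SAP text. No new data are needed.
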